services that serve heroin users.³⁰ The sole exception to this is one program that used this model in primary care to provide naloxone to family members of patients who are prescribed OAs.³¹ Extant evidence for these programs is observational. Additionally, although it has been established that overdoses among heroin users are often witnessed,²⁹ it is unknown how often OA overdoses among pain patients occur in the presence of others. A recent cost-effectiveness analysis predicted that, even if 20% of the heroin users in a community were trained in naloxone distribution, only 6% of heroin overdoses would be prevented.³² These data suggest the need for complementary approaches aimed at reducing an individual's overdose risk behavior. Although the recent initiative to provide naloxone to VHA patients recommends that providers complement the naloxone training with patient education, this education has not been tested, and may not be sufficient for altering substance use-related behaviors.

Relevant conceptual models. The intervention will be studied as a selective prevention program, in that participants will be on long-term OA therapy and have a risk indicator for overdose (moderate to high dose). Overdose death, a highly significant but relatively rare outcome, would not be an appropriate primary outcome. Instead the primary outcomes will be overdose risk behavior and OA use (aberrant use or pattern of increasing dose), and secondary outcomes are self-reported non-fatal overdoses, other OA-related adverse events, functioning, and safe OA handling.

Our framework is informed by Ballantyne & Mao's model of adverse effects of OAs. Repeated OA use leads to pharmacological tolerance and increased pain sensitivity, both of which contribute to apparent tolerance, and a need, or perceived need, for a dose increase. We add that OA tolerance and pain sensitivity increase the likelihood of aberrant use, which in turn also leads to dose increases, and subsequent adverse outcomes. The development of tolerance and dose increases can lead to overdose risk behaviors (e.g., consuming a high total dose, breaks in use with resumption of normal use). These processes can be cyclical. Additionally, reducing the proportion of patients on potentially unnecessarily high doses of OAs is a goal of the Opioid Safety Initiative. The proposed intervention may provide a complementary approach by decreasing factors that lead to dose escalations and aberrant use.

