Relevance to VA health care. Approximately half of VHA patients experience pain on a regular basis.⁷¹ Among OEF/OIF/OND Veterans, pain is among the most common symptoms reported.⁷² OA therapy constitutes a primary modality of chronic pain treatment and is the focus of many treatment guidelines.^{1,22} In a study of VISN20 patients with persistent pain in 2008, 72% were prescribed an OA at least once in the year.³ Pain in Veterans is generally associated with poor functioning and more psychiatric problems.^{71,73,74} Methods to maintain historical gains in pain care access while reducing the potential harms are essential to the quality of life of VHA patients.

Prior research by study team members has demonstrated that VHA patients are at an elevated risk of unintentional overdose compared to the general U.S. population.⁶ Analysis conducted by the study team found that there were 12,233 overdose deaths among VHA patients between 2001 and 2009. Reliable estimates of the number of non-fatal overdoses are difficult to determine from VHA medical records alone, but CDC data indicate that there were 22.9 non-fatal overdoses treated in EDs for every fatal overdose in the U.S. during this time period.⁷⁵ Consequently, there were an estimated 280,136 non-fatal overdoses serious enough to merit ED treatment among VHA patients between 2001 and 2009.

The VA Uniform Mental Health Services Handbook requires that "primary care, medical specialty, and mental health services ... use case-finding methods to identify patients who ... misuse prescription or over the counter agents." The proposed study will further this goal by providing data on an intervention that can be implemented with patients who have pain and are engaged in aberrant use of OAs. Ultimately, the proposed project could lead to reductions in overdose mortality among VHA patients.

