OAs Prescribed. We will determine prescribed OA regimen from pharmacy data using established methods¹² with standard morphine equivalency ratios.¹¹ The Medication Possession Ratio (MPR)⁸² will also be used to measure actual medication use/adherence by accounting for early and late refills. The MPR can identify patients who consistently refill early, an indication of overuse. OA therapy outside of VHA will be assessed and those participants who report being prescribed OAs by non-VHA care providers will be asked about formulation, dose, and prescribed schedule, and the dose and MPR will be adjusted accordingly. Pharmacy data will also be used to determine prescribed dose for the eligibility criteria of 20 MEM/day.

Aberrant OA Use. The Current Opiate Misuse Measure (COMM) is a 8-item self-report of recent aberrant use developed for, and validated in, patients receiving OAs.⁶⁵ Items include: getting medications from someone other than the prescribing physician, taking medications differently than prescribed, and taking for reasons other than pain. Patients report their past-month behavior on a five-point Likert scale ($\alpha = 0.86$).

Overdose Risk Behaviors. We have adapted items on overdose risk (ORB) from Strang and colleagues²⁶ by adding risk factors specific to OAs.^{12,18,33,83} This measure was developed with a national consortium of experts. Items include: high dose (more than 100 MEM/day); combining OAs with other substances; route of use; using alone; and returning to usual dose after a period of abstinence. In our pilot RCT, this measure was able to detect substantial between-subject variation, with participants reporting between 0 and 10 behaviors, 70% reporting at least one risk behavior, and a mean number of behaviors of 1.9 (S.D.=2.0).

Secondary Outcomes.

Non-Fatal Overdose Experiences: Established items will be used to assess non-fatal overdose (OESWA and OESWD).⁸⁴ For each overdose, we will assess the date, substances involved, intent (categories including “suicide attempt,” “did not want to die but did not care about the risks,” “accident, effect of drug was not expected,” and “unsure”), preceding events, and actions taken by others.

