Treatment Use (including ED): Use of specific types of clinical services will be assessed with questions adapted from the Treatment Service Review (TSR).⁸⁵ For ED use, participants will be asked “how many times did you visit an emergency room?” and asked what were the problems for which they were seeking treatment and the date of each visit. Parallel questions will assess non-VHA use of addictions, pain, and mental health services. We will assess alternative pain treatment (AT) modalities utilized during baseline and a more extensive list of pain treatments and self-management strategies during follow-up assessments.

Injuries: The Revised Injury Behavior Checklist (RIBC) for adults⁸⁶ will be used to identify 4 types of injuries, including those not resulting in use of ED services (overdose will be excluded from this measure).

Over-sedation: Pain Treatment Satisfaction Scale (PTSS)⁸⁷ is a 12-item tool designed to assess the OA-related side effects on a scale of 0 (“Did not experience” to 5 (“Extremely bothered”). Over-sedation will be measured as “Excessive fatigue”, “inability to concentrate”, and/or “drowsiness.”

Safe Storage and Disposal of OAs: We will adapt items by McCauley and colleagues⁸⁸ designed to assess knowledge of safe storage and disposal of OAs. This measure is sensitive to the effects of a web-based psychoeducation on safe OA storage and disposal.

Functioning: We will use the first item from the Veterans RAND 12-item Healthy Survey (VR-12)⁸⁹. In the interest of reducing patient burden, we will use the single item. This is consistent with health status items

used in many national health studies^{90, 91}.

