Medical Chart and Administrative Data Extraction. Data will be extracted from the CDW Production Domains, and CDW MCA (formerly DSS) NDE, MedSAS Files including VetsNet Files and CAPRI/VistAWeb datasets as well as the Opioid Therapy Risk Report (OTRR). The OTRR allows VA providers to efficiently monitor clinical data related to opioid pain treatment within the electronic medical record (EMR). The OTRR provides a list of patients on long-term opioid therapy with upcoming primary care appointments, along with related opioid risk factors. Opioid pain medications will be requested from CDW MCA NDE pharmacy data. Dates of fills, day supply, prescribing physician, total quantity and dosing and schedule instructions will also be used. We will collect basic demographic information (name, birthdate/age, race, social security number), OEF/OIF/OND service, diagnosis (e.g., terminal cancer), clinic appointment information (date of appointment, type of appointment, etc.), and basic contact information (address, phone numbers) for those receiving long-term OA therapy treatment. These data will be extracted from the staff, patient, appointment, inpatient, outpatient and pharmacy CDW Production Domains, MedSAS Files and/or the OTRR. CAPRI/VistAWeb will be used to check for external appointments. Research staff will confirm upcoming appointment and eligibility. Access to real SSN data is needed in order to link the administrative data from the MedSAS datasets, CDW and OTRR to data from chart reviews. In addition to OA regimen, data will be extracted over follow-up to assess VHA service use, diagnoses, mental health assessments, other medication use, and mortality (from the Beneficiary Identification Records Locator Subsystem of Vital Status; mortality will also be measured by information that comes from the contacts nominated by that participant or records databases and obituary listings). VHA service use, diagnoses, mental health assessments, and other medication use will be extracted from CDW Production Domains, MedSAS files and CAPRI/VistAWeb. We will also examine the chart for information related to the prescriber notification in order to better understand the impact of the notification process. We will use both VINCI and our local VA server for the administrative data extraction of potential patients that fit our eligibility criteria. The use of both storage options will increase our ability to find potential patients in a timely manner and avoid delays due to occasional problems with the transfer of data from VINCI to our local VA server. The OTRR will be saved to our local VA server.

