Aim 1 analyses. Hypothesis 1: Participants randomized to the intervention condition will report fewer overdose risk behaviors than EUC participants at follow-up. The overdose risk behavior is conceptually a composite count of number of behaviors. However, prior to initiating modeling, we will examine the distribution of responses to individual items on the overdose risk behavior assessment as well as the distribution of the overall composite count. Primary analyses will consist of GLMs to examine group (Intervention vs. EUC) as the primary independent variable at each time point and a GLMM to examine the average effect of the intervention over all assessments. If GLM findings suggest that the impact of the intervention may vary by assessment period, this will be examined using a time by group interaction term.

Aim 2 analyses. Hypothesis 2a: Participants randomized to the intervention condition will have lower average MEM/day doses and MPRs than EUC participants over follow-up. Hypothesis 2b: Participants randomized to the intervention condition will report lower levels of aberrant OA use than EUC participants over follow-up. Aim 2 dependent variables will include both objective measures based on pharmacy data and self-reported aberrant use. Prescribed OA dose will reflect escalating doses (likely due to patient request) and high total doses after combining regularly scheduled and "as needed" OAs.¹² An MPR⁸² greater than 1 identifies potential overuse based whether new fills frequently occur before the days supplied by a prior fill have elapsed. The distribution of the daily dose, MPR, and COMM scores will be examined to select appropriate models. The same analysis strategy used to test intervention effects in GLMs and GLMMs for Aim 1 will be used for the dependent variables in Aim 2.

Secondary aim 1 analyses. Hypothesis 3: Participants randomized to the intervention condition will have fewer non-fatal overdoses, fewer injuries and other OA-related adverse events, and better OA storage and disposal behaviors and better functioning than EUC participants. Analysis will follow the general GLM and GLMM framework used in the Aims 1 and 2 analyses, but a survival analysis approach using Cox proportional hazards regression modeling will also be used to examine time-to-event data (non-fatal overdoses and emergency department visits).

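### The overdose and ED-visit endpoints rest on self-report and count only non-fatal overdoses, although VHA service-use, diagnosis and mortality data are already being extracted

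*Combined protocol and SAP*

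**What the plan says.** The Background (Relevant conceptual models) states that "secondary outcomes are self-reported non-fatal overdoses, other OA-related adverse events, functioning, and safe OA handling". In the Measures section, under Secondary Outcomes, the overdose instrument is a questionnaire: "Established items will be used to assess non-fatal overdose (OESWA and OESWD". Under Treatment Use, ED visits come from an item adapted from the Treatment Service Review that asks "how many times did you visit an emergency room" and requests the date of each visit. Follow-up questions refer to the time since the previous assessment.

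Secondary aim 1 analyses (Hypothesis 3) repeats the non-fatal restriction. It applies the general GLM and GLMM framework and adds Cox regression to "examine time-to-event data (non-fatal overdoses and emergency department visits". It names no data source, censoring date or rule for death.

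Under Medical Chart and Administrative Data Extraction, the plan says that "data will be extracted over follow-up to assess VHA service use, diagnoses, mental health assessments, other medication use, and mortality", with mortality drawn from a VA vital-status system, nominated contacts, databases and obituaries. Sources of Materials adds, in general terms, that objective data will come from clinical records. No section assigns these data to the overdose or ED-visit endpoints.

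**The concern.** A participant who overdoses, is admitted or dies may be unable to answer the next survey because of that event. If the survey is the only source, the participants whose outcomes matter most for this comparison are the likeliest to be unobserved. In the Cox model that is potentially informative censoring. In the GLM and GLMM analyses it strains the missing-at-random assumption. The plan offers a pattern mixture model if that assumption is untenable, but gives no criterion for deciding so and no counterpart for the Cox model.

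The gravest form of the harm that the intervention targets is also outside the endpoint by definition, even though deaths are ascertained. Adverse-event reporting does not fill the gap: its table lists overdose-related ED visits and hospitalisations as expected and not reported to the IRB, and although deaths are reportable, no comparison by arm is planned. The number needed to treat and the therapist time per adverse event prevented (Additional analyses) would carry the same limits.

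One further inconsistency bears on this. The Patient safety section withdraws participants found at serious imminent risk of opioid-related self-harm and leaves them out of analysis. The Safety Monitoring Plan instead speaks of a sensitivity analysis for the impact of such cases. The two sections must be reconciled, because the first removes high-risk people from the harm comparison.

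**Working it through.** **The plan's own figure.** Power analysis: 450 × 0.80 = 360 analysed, 180 per arm. This reproduces. The plan states no event rate, target hazard ratio or power for overdose or ED visits, so what follows uses labelled assumptions.

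**1. Participants without a 12-month survey.** 450 × 0.20 = 90.

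**2. Share of events they hold.** Let their risk be k times that of responders. The share of events in the window covered by the 12-month survey is 0.2k / (0.8 + 0.2k).
- k = 1: 0.2 / 1.0 = 20%.
- k = 2 (assumed): 0.4 / 1.2 = 33%.

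For 12-month totals these shares are upper bounds at the given k, because the 3- and 6-month surveys capture some earlier events. A missed earlier wave can also be recovered later, since each survey looks back to the previous assessment.

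**3. In numbers of events.** At an assumed 12-month risk of 5%, 10%, 20% or 30%, the 90 would have 4.5, 9, 18 or 27 participants with an event at k = 1, and twice that at k = 2. The same upper-bound caveat applies.

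**4. Precision.** At an assumed 10% risk and k = 1, responders supply 360 × 0.10 = 36 events and all randomised participants 450 × 0.10 = 45. By Schoenfeld's formula, with an assumed hazard ratio of 0.5, power is about 55% with 36 events and 64% with 45; 80% needs 66. Records would recover only part of the difference.

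**5. Between-arm ratio.** With 20% lost in each arm and the same k in both, the true overall risks are both (0.8 + 0.2k) times the responder risk, so the ratio is unchanged. Bias in the ratio needs the link between loss and events to differ by arm. The documents give no figure for that, so no direction or size of bias can be stated.

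**6. Absolute risk.** At k = 2 the overall risk is 0.8 + 0.2 × 2 = 1.2 times the responder risk. With the same relative effect in responders and non-responders, the true risk difference is also 1.2 times the responder-only one. A responder-only number needed to treat would then be 1.2 times too large. At k = 1 there is no such distortion.

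**7. Fatal overdoses.** Relevance to VA health care gives 22.9 ED-treated non-fatal overdoses per death. The fatal share is 1 / (1 + 22.9) = 4.2%. It is lower still if self-report also picks up overdoses not treated in an ED, so about 4% is a ceiling on this ratio.

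**The case against.** The strongest reply is that the plan is silent here, not wrong. A reader might infer that a participant who dies or is lost is counted as having had no event, or even as a success. The documents do not support that. No section scores such participants as event-free. A Cox model would ordinarily censor them at last contact or death, and the Analysis plan uses partial data under missing at random, with pattern mixture or imputation as fallbacks.

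A reader might also infer that the VHA records are deliberately left out. That too goes beyond the text: Secondary aim 1 analyses names no source, and Sources of Materials mentions clinical records soon after listing overdoses and adverse events. Nor is response limited to those who come back to the clinic, since Data collection procedures allows phone, mail and community contact. All of this stands and sets the limits of the point.

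Two reasons could be offered for the present definitions. The first is that "Reliable estimates of the number of non-fatal overdoses are difficult to determine from VHA medical records alone". The last word of that statement matters: it argues for combining sources, and it does not concern VHA ED visits. The second is that overdose death is rare. The Background uses that argument only about the primary outcome. The Dissemination Plan does suggest a larger future study for fatal and non-fatal overdose, and the 4% ceiling confirms that deaths would be few. Rarity limits what deaths add to power; it is no reason to leave ascertained overdose deaths out of an overdose endpoint.

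Combining sources also has precedent in this protocol: under OAs Prescribed, pharmacy-based dose is adjusted with self-reported non-VHA prescriptions.

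**Conclusion.** The point holds as a cheap improvement to secondary endpoints for which no power is stated. Followed as written, a fatal overdose is never an event, and an overdose or ED visit in a survey non-responder is unobserved even where VHA records would show it. The handling of death and loss, and the role of the extracted records, are unstated.

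Non-response is the larger gap: 90 of 450 at 12 months, holding about 20% of the events in the affected window at equal risk and 33% at an assumed doubled risk. Fatal overdoses add at most about 4%. The documents do not show that the arm comparison is biased in either direction. That would need loss to be linked to events differently in the two arms, and nothing in the plan suggests it.

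**What to change.** In Secondary aim 1 analyses:

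- Define ED visits as VHA-recorded visits for all randomised participants through month 12, plus self-reported visits, de-duplicated by date.
- Define overdose as any overdose, fatal or non-fatal, that is self-reported or found in the extracted VHA diagnosis, ED, inpatient or mortality data.
- Treat other deaths as a competing event, and state the censoring date for each source.
- Add a sensitivity analysis that counts deaths of unknown cause as overdose events.
- Report two further sensitivity analyses: records only, where ascertainment does not depend on completing surveys, and self-report only.
- Report all-cause deaths by arm.
- Reconcile Patient safety with the Safety Monitoring Plan on withdrawn participants, and keep them in the records-based analysis where consent allows.

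The cost is an amended endpoint definition, a date-matching rule and programming on data already being extracted. Some limits remain. Non-VHA events in non-responders are still missed, and cause of death may be unknown. Because responders have two sources and non-responders one, the combined endpoint still depends partly on retention; the records-only version is there for that reason.

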Intervention. The intervention session is tailored on knowledge, values, concerns, barriers, and skills/tools for managing pain. It combines elements of ME and cognitive behavioral therapy (CBT) and uses the structure of ME brief interventions. Participants are presented with a variety of risk reduction strategies, including abstinence of all substances except prescribed medications, not combining substances, and taking medications as prescribed. Participants are provided with a number of strategies for coping with pain that may reduce reliance on OAs, such as meditation, activity pacing, stretching, exercise, ice or heat, eliciting support from friends and family, and distraction. The therapist prompts the patient to reflect on which tools are likely to help him/her personally, barriers to using those tools, and plans for overcoming those barriers. The intervention does not recommend that participants stop or reduce their OA use below prescribed levels, but participants who express concern that the benefits of OAs may be outweighed by the harms are guided on how to discuss this concern with their prescriber. The session includes the following organization:

Explore: 1.) Introduce purpose of the session, affirm autonomy to make decisions; 2.) Elicit participants' strengths, values, and goals. 3.) Guide discussion of tailored behavioral history (OA use, other drug and alcohol use, overdose risk behaviors) and pain experiences using open-ended questions/probes.

Guide: 1.) Review role of cognitive factors in pain; 2.) Review risk factors for overdose, with particular emphasis on risk factors for OA overdoses, using an "elicit-provide-elicit" approach;¹⁰ 3.) Review other risks of OA use (oversedation and resulting injuries, impaired driving) and safe storage and disposal; 4.) Guide discussion of potential changes to risk behaviors and use of tools, using menus/lists, eliciting benefits of change, reflective statements, clarifying ambivalence, and anticipating and discussing barriers to change; 5.) Use confidence rulers to elicit importance, confidence, and intention to change.

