
Mediators and process measures. (*Baseline, Post-Test and Follow-up, except where noted*)

Knowledge of Overdose Risk Factors. Knowledge of overdose risk factors (OK) will be assessed with a checklist adapted from prior studies²⁶ with additional items for OA overdose specifically (OEND). In our pilot RCT, 56% of participants misidentified at least one risk factor. In addition, at Baseline and Follow-up, we will assess participant's involvement in overdose education and naloxone distribution.

Motivation and Self-Efficacy. Behavioral intentions (motivation; BI), self-efficacy, and readiness (SEOS) to change will be measured with 6 visual analog rulers.⁹² These constructs are considered critical to ME interventions.¹⁰

Perceived Satisfaction and Utility (Post-test only). A five-point Likert scale (from "really didn't like it" to "liked it a lot") will elicit satisfaction (PSU-I & C).⁹³ We will use similarly-structured questions⁹⁴ to measure the perceived helpfulness of specific intervention components.

Other factors. (*Baseline and Follow-up, except where noted; collected to inform later implementation, to characterize study sample, and/or to examine moderators of effect*)

Suicidality. We will use select modified items (3) from the National Comorbidity Survey (NCS⁹⁵) that will assess past 12 month suicidal ideation and suicide attempts. Follow-up assessments will inquire about the time since last assessment.

Driving after consuming OAs. For our prior work, we adapted items from the National Survey of Drinking and Driving Attitudes and Behaviors⁹⁶ to OA use (included in ORB). Frequency is assessed with a 5 point Likert scale.

Pain Severity and Functioning. We will use select items (7) from the Brief Pain Inventory-Short Form (BPI)⁹⁷ to assess pain interference on a 11-point numeric rating scale (0=Does not interfere, 10=Completely interferes). The Pain, Enjoyment and General Activity scale (PEG)⁹⁸ is a 3-item questionnaire designed to measure chronic pain in a primary care setting. The Centrality of Pain Scale (CPS)⁹⁹ is a 10-item scale used to assess how patients perceive the role of chronic pain in their lives. The CPS has high internal consistency (Cronbach's alpha = .902).

Alcohol and Drug Use Severity. The Addiction Severity Index (ASI)¹⁰⁰ will be modified to allow participants to self-administer the questionnaire. We will use select items (7) from the ASSIST (WHO¹⁰¹) to assess alcohol use and problems.

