Secondary Aim 2 analyses. Hypothesis 4a: The effect of the intervention on overdose risk behaviors and OA use will be mediated by post-intervention self-efficacy and motivation to change. Hypothesis 4b: OIF/OEF/OND status and baseline psychiatric distress will moderate the effect of the intervention on overdose risk behaviors and OA use. Mediators: In further analysis of the GLMs and GLMMs developed for Aims 1 and

2, we will include potential mediators in additional models and examine changes in effect size for the group indicator. Following the recommendations of Preacher and Kelley¹⁰³, we will use a κ^2 statistic to estimate the effect size and conduct significant testing of the mediation. *Moderators*: An interaction effect between each hypothesized moderator and the group indicator (intervention vs. EUC) will be specified in separate GLMs. For longitudinal analysis, we will examine baseline moderator by group interactions in GLMMs.

Additional analyses. We will examine descriptive statistics of the “perceived satisfaction and utility” measure from the post-test for further refinement of the intervention materials for follow-up. Descriptive statistics will also be used to examine differences between those who participated and those who refused participation of select characteristics. The focus group interviews conducted with prescribers will be entered into NVivo 10. [name] and the coordinator will independently read transcripts and use an iterative process to develop a coding scheme. Final codes will be grouped conceptually into meaningful themes and sub-themes. We will also calculate the number needed to treat to prevent one adverse event and amount of therapist time needed to prevent one adverse event.

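### The mediation plan does not specify adjustment for baseline motivation, baseline self-efficacy or the baseline outcome, so the indirect effect can be biased in either direction

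*Combined protocol and SAP*

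**What the plan says.** Hypothesis 4a, under Secondary Aim 2 analyses, reads: "The effect of the intervention on overdose risk behaviors and OA use will be mediated by post-intervention self-efficacy and motivation to change". The mediator is therefore a level after the session, not a change. As to method, "we will include potential mediators in additional models and examine changes in effect size for the group indicator", and a kappa-squared "statistic to estimate the effect size and conduct significant testing of the mediation".

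The models being extended are those of Aims 1 and 2. Under Aim 1 analyses, "Primary analyses will consist of GLMs to examine group (Intervention vs. EUC) as the primary independent variable at each time point", together with "a GLMM to examine the average effect of the intervention over all assessments". Aim 2 uses the same strategy. Group is the only predictor named, apart from a possible time-by-group term.

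The Analysis plan has one covariate-adjustment rule: the arms are compared on key variables, and a variable is adjusted for if the arms differ significantly on it.

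Baseline values of the mediators will exist. Behavioral intentions (BI), self-efficacy and readiness (SEOS) "will be measured with 6 visual analog rulers", and the heading of that section gives the timing as "Baseline, Post-Test and Follow-up, except where noted". The measures table also schedules both instruments at baseline. Data collection procedures describes the post-test as measuring change in these constructs. That purpose does not reach the mediation analysis.

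**The concern.** Mediation needs two links: arm to mediator, and mediator to outcome. Randomisation secures the first. It does nothing for the second, because nobody is randomised to a level of motivation. A patient who arrives motivated will tend to be motivated at post-test, and may have a different outcome for reasons that predate the session. If only the post-test level is in the model, that existing association is read as an effect of the mediator. Multiplied by the session's shift in the mediator, it becomes an indirect effect.

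The imbalance rule cannot repair this. The confounding is between patients within each arm and is present even when the arms are perfectly balanced at baseline.

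What is at stake is the reading of Hypothesis 4a. Under Contributions of the proposed work, the protocol says the mediator results can inform theoretical models of brief interventions and behavior change. A biased indirect effect would feed into that.

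**Working it through.** **Inputs from the plan.** Analysed n: 0.80 × 450 = 360, 180 per arm; two-sided alpha 0.05 (Power analysis). The plan gives no power or error rate for mediation. Its figure for continuous outcomes is 80% power at a standardised effect of 0.30. Reproduced: SE = √(2/180) = 0.1054; 0.30/0.1054 = 2.846; Φ(2.846 − 1.96) = 81%. This agrees, and the same figure is the power of the arm-to-mediator test when the shift is 0.30 SD.

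**Assumed inputs.** The documents give none of these:
- a: session effect on the mediator, in SD.
- ρ: baseline-to-post-test correlation of the mediator within arm.
- γ: association of the baseline mediator with the later outcome, in SD.

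**Bias with no true mediation.** Let M1 = ρM0 + aG + error, with unit variance within arm, and Y = γM0 + error. Regressing Y on G and M1 without M0 gives M1 a slope of ργ, although its true effect is zero. The spurious indirect effect is a × ρ × γ. At a = 0.3, ρ = 0.6, γ = −0.3 this is −0.054. The simulated mean was −0.054. The group coefficient moved from 0.000 to +0.055 when the mediator was added, so examining the change in that coefficient picks up the same artefact.

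**False-positive rate.** Under a joint test of both paths, the rate is approximately the power of the a-path test times the power to detect a slope of ργ, whose SE is about √(1 − (ργ)²)/√360. In the central case: slope 0.18, SE 0.0519, z = 3.47, power 93%; 0.81 × 0.93 ≈ 76%.

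| a | ρ | abs. γ | abs. a×ρ×γ | By formula | Simulated |
|---|---|---|---|---|---|
| 0.3 | 0.5 | 0.15 | 0.023 | 24% | 23-25% |
| 0.3 | 0.6 | 0.20 | 0.036 | 51% | 51-52% |
| 0.3 | 0.6 | 0.30 | 0.054 | 76% | 76% |
| 0.4 | 0.7 | 0.30 | 0.084 | 95% | 94% |
| 0.3 | 0.6 | 0.05 | 0.009 | 7% | about 8% |
| 0 | any | any | 0 | at most 5% | at most about 4-5% |

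**Count outcome.** With a Poisson-type outcome of mean 1.9, a = 0.3, ρ = 0.6 and a rate ratio of 0.80 per SD of baseline motivation, 0.3 × 0.6 × ln(0.80) = −0.040. The simulated value was −0.040, with 76% false positives.

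**Direction.** With a rate ratio of 1.25 per SD, ln(1.25) = +0.223 and the spurious effect becomes +0.040. If a true mediator effect b exists, the unadjusted slope is b + ργ. For example, b = −0.18 with ρ = 0.6 and γ = +0.3 gives −0.18 + 0.18 = 0, and real mediation disappears.

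**After adjustment.** With the baseline mediator in both models, the mean indirect effect was at most 0.002 in absolute value. False positives were about 3-7% across a = 0.2 to 0.5 for continuous outcomes, and about 4-5% for counts. Adding only the baseline outcome helped little in the count model (76% to 73%). In linear runs it still left 11-56%. The baseline mediator is the essential covariate.

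**The case against.** **The plan is silent; it does not exclude baseline values.** This stands. No covariate list is given. The GLMM covers all assessments, and baseline is counted among the five assessments, so the baseline outcome may enter as a repeated measure. A reader might infer a decision to leave baseline out, but the documents show only that it is not specified. A baseline outcome treated as a repeated measure would still leave the baseline mediator out.

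**The bias is conditional.** This also stands. Motivated patients are balanced across arms in expectation, so false mediation needs both a shift in the mediator and a baseline association. Shifting motivation and self-efficacy is the intervention's intended mechanism, but the documents quantify neither input.

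**The direction is unknown.** A reader might assume that motivated patients have fewer risk behaviors. The instruments measure intention and readiness to change, and patients with more risk behavior may have more to change.

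**The plan does not name a joint-significance test.** True, and the rate depends on the test: a Sobel test gives 58% where the joint test gives 76%. If a significant total effect were also required, a null trial would pass both in about 4% of runs. With a true direct effect of −0.3 SD, it would do so in 64%.

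**Ruler echo.** One might go further and argue that the session step "Use confidence rulers to elicit importance, confidence, and intention to change" contaminates the post-test rulers. The documents do not show that the items are shared or fix the interval between them (a later call-back is allowed), and the size cannot be estimated. Replacing the mediator with 3-month scores would change Hypothesis 4a, and the post-test already precedes every follow-up outcome. Neither is part of this point.

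**Conclusion.** The omission is real and worth correcting. As written, the mediation models need not contain the covariate that would remove confounding by pre-existing motivation, and the imbalance rule does not supply it. The bias in the indirect effect is roughly a × ρ × γ: 0.023 to 0.084 SD in absolute value over the assumed range, with joint-test false positives of about 23-94%. That range rests on assumed inputs. It falls to about 8% at an association of 0.05, and to the nominal level or below if the session does not move the mediator.

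A reader might infer that Hypothesis 4a would probably be declared supported in error. The documents do not support that: neither the strength nor the sign of the baseline association is known, and the bias could equally hide real mediation. The supportable conclusion is that the indirect effect could not be interpreted with confidence. The point concerns a secondary, explanatory aim.

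**What to change.** In Secondary Aim 2 analyses, state that every mediation analysis adjusts for the baseline value of the mediator (BI or SEOS, as applicable) and the baseline value of the outcome, in both the mediator model and the outcome model, whether or not the arms differ at baseline. For the GLMM, say whether the baseline outcome is a covariate or a repeated measure.

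Add a sentence that unmeasured mediator-outcome confounding may remain after this adjustment. The near-zero bias after adjustment in the simulations reflects a set-up in which baseline motivation was the only confounder.

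The cost is analysis-plan wording. All the variables are already scheduled at baseline, and no visit, instrument or sample-size change is needed.
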